cognitive or medical limitations per clinician report, (5) possess a cellphone, and (6) able to give consent. *Adolescents living with HIV (ALH) between the ages 12-17 will also be eligible to participate in focus groups and cognitive interviews as part of a separate component of the Development Phase. Their eligibility criteria is as follows:* (1) *read English and speak English or a local language spoken by clinic staff (e.g., Twi),* (2) *in medical care for HIV and receiving ART at our clinic,* (3) *aware of their HIV status as per parent/guardian report,* (4) *not impaired by cognitive or medical limitations per clinician report,* (6) *able to give assent, and* (7) *their parent/guardian is able to give consent. Parents or guardians of ALH are also able to participate in focus groups and cognitive interviews as part of this separate component. Parent eligibility is as follows:* (1) *speak English or a local language spoken by clinic staff (e.g., Twi),* (2) *own a mobile phone,* (3) *aware of their child's HIV status,* (4) *not impaired by cognitive or medical limitations per clinician report, and* (6) *able to give consent.* Participants in the randomized pilot must have also demonstrated a recent detectable viral load. Study staff will NOT make changes to ART regimens and participants will be encouraged to speak with their doctor if they have concerns about their medications or side effects of these medications. Any unexpected ethical issues that arise with our participants will be discussed immediately with the PI. All participants will receive a resource packet including information on ART as well as references to local health and social services. We will also encourage participants to identify a treatment monitor to take part in the game. This will not be a requirement for our study, however, because those who begin playing the game without a monitor will be incentivized via game rewards to recruit one (and we will assess this occurrence). Participants without a monitor will be assigned a peer educator to fill this role. Inclusion criteria for treatment monitors includes: 1) *read English and speak English or a local language spoken by clinic staff,* (2) *target HIV patient has agreed to their participation,* (3) *aware of target patient's HIV status as per patient report,* (5) *possess a cellphone, and* (6) *able to give consent.*

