Exclusion criteria. Individuals will be excluded if they meet any of the following criteria: (a) self-reported participation in another ART adherence-related study (YPLH only) or (b) unable to understand the consent process.

Sample, site/recruitment, and retention. We will recruit 24 YPLH and potentially 24 treatment monitors for the iterative open trial, and between 5-40 YPLH for the youth advisory group, as part of the Development Phase. The advisory board ranges from 5-40 participants because those who attend the first group meeting will be invited back to attend two to four additional meetings. However, if they are unable to attend, new participants will be added to the group. *We will also recruit 12-16 ALH and 12-16 parents/guardians of ALH for focus groups and 10 parent-ALH dyads for cognitive interviews, as part of the Development Phase.* Sixty 60 YPLH, and potentially 30 treatment monitors, will be recruited for the pilot. In the pilot, it is estimated that 70% of youth will be female given that females account for 58% of all HIV cases in Ghana and seek treatment more than males (5). About 25% of YPLH will be newly-initiated to ART. Efforts will be made to equally sample young people who acquired HIV perinatally and behaviorally. Site/recruitment: Participants will be recruited from the HIV care clinic (the Clinic) at the Komfo Anokye Teaching Hospital (KATH), a teaching hospital affiliated with the Kwame Nkrumah University of Science and Technology (KNUST) located in Kumasi. It is the second largest clinic in the country and has a patient population estimated at 4,000. Although no research activities involving human subjects will occur at Rhode Island Hospital (RIH; the co-PI's institution), RIH will support KNUST and KATH with compliance on regulatory matters, including authoring the standard operating protocol, IRB applications and approvals, quality control, and data analysis. Retention techniques: routinely updating contact information, reminder phone calls, online monitoring of game interactions, maintaining records of friend/family contacts, and obtaining an emergency contact.

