Identifying eligible patients and consent procedures. Eligible patients will be identified by clinic and research staff involved with the project. All eligible YPLH will be recruited consecutively until our desired sample size is obtained. Research staff including the Research Assistant and Project Coordinator will conduct the informed consent in a private clinic room.

Development Phase (Aim 1)

The goal of the Development Phase is to create our Text-Based Adherence Game using a two-step approach: youth advisory board meetings followed by an iterative open

trial. The youth advisory board will be made up of five to eight YPLH. Findings from each step of this phase will be presented at board meetings held three to five times. Audio from board meetings will be digitally recorded. A working group will also be established consisting of the Project Coordinator, a clinic staff member, and the PI and Co-PI's. The working group will meet regularly for the entire project to oversee study implementation.

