Measures: Participants' overall satisfaction with the game will be assessed using a modified version of the Client Satisfaction Questionnaire (CSQ-8) after each iteration. The CSQ is an 8-item measure with good reliability and validity and used previously with African samples (46). They will also complete a modified Session Evaluation Form (SEF), which has 13 items that reflect areas of feasibility and intervention utility. Participants will complete measures of main study outcomes using an audio-assisted computer self-interview (ACASI). Main outcome measures are listed in the next section. The last prototype will be reviewed and revised by the research team before being finalized. **Training of Research Assistants (RAs), Fidelity Monitoring, and Supervision:** RAs will be trained by the co-PI ([name]) over a period of two days to provide

game instructions. Game instructions will be audio-recorded and coded for fidelity. Problems with fidelity will trigger retraining of RAs by the PI. Peer educators will receive in-person supervision from study staff who will themselves receive Skype supervision from the [name]. [name] will also monitor participants' game activity daily via the system's website.

Randomized Controlled Pilot Phase (Aim 2)

We will evaluate the preliminary impact of the Text-Based Adherence Game run for one year compared to a control group. The pilot will include 60 YPLH on ART with the same eligibility criteria as the open trial. The same procedures will also be used pending open trial feedback. The game will be evaluated via a baseline and two follow-up assessments (6-/12-months post-baseline). Randomization will occur after enrollment using a random number generator. Participants not randomized to the Text-Based Adherence Game will receive the SOC condition as described above. See Figure 4.

Figure 4. Steps for Aim 2 Randomized Controlled Pilot

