6. “There are people in my life that are supportive about avoiding alcohol use” _____

Modified Social Provisions Scale

Instructions

The next set of questions are about a particular person who you rely on the most for helping you with your HIV treatment on a daily basis. This person is typically a friend, parent or other family member, or your treatment supporter (also known as a treatment buddy) but they can also be a peer educator, clinic counselor, or someone else. He or she may remind you to take your medication, make sure you get to your HIV clinic appointments, or help you in other ways. Please identify this person:

- 1- Treatment supporter (treatment buddy)
- 2- Same-age or younger friend
- 3- Older adult friend
- 4- Parent
- 5- Other family member (Please describe your relationship to this person: _____)
- 6- Peer educator
- 7- Clinic counselor
- 8- Someone else (Please describe your relationship to this person: _____)

I'm going to ask you about your relationship with this person. Please tell me how much each statement describes your situation by using these responses. So, for example, if you feel a statement is VERY TRUE you would say Strongly Agree. If you feel a statement CLEARLY does not describe your relationship, you would answer Strongly Disagree?"

Strongly Disagree = 1

Agree = 3

Disagree = 2

Strongly Agree = 4

1. This person will help me if I really need it.
2. I do not have a close relationships with my this person.
3. I can't turn to this person in times of stress.
4. This person calls on me to help him/her.
5. This person likes the same social activities I do.
6. This person does not think I am good at what I do.
7. I feel responsible for taking care of this person.
8. This person thinks the same way I do about things.
9. I do not think that this person respects what I do.
10. If something went wrong, this person would help me.
11. I have a close relationship with this person that make me feel good.
12. I can talk to this person about decisions in my life.
13. This person values my skills and abilities.
14. This person does not have the same interests and concerns as me.
15. This person does not need me to help take care of them.
16. This person is a trustworthy person I can turn to if I have problems.
17. I feel a strong emotional tie with this person.
18. I cannot count on this person for help if I really need it.
19. I do not feel comfortable talking about problems with this person.

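### The eligibility rules do not stop a standard-of-care pilot participant from being consented as a game-arm patient's treatment monitor

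*Combined protocol and SAP*

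**What the plan says.** Under Methodology, Inclusion criteria, staff will "encourage participants to identify a treatment monitor to take part in the game". A monitor is not required, but "those who begin playing the game without a monitor will be incentivized via game rewards to recruit one", and anyone without one is assigned a peer educator. The monitor criteria cover language, the patient's agreement, being "aware of target patient's HIV status as per patient report", a cellphone and ability to consent.

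Under Exclusion criteria, item (a) is "self-reported participation in another ART adherence-related study (YPLH only"), and item (b) is inability to understand the consent process.

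The sample section plans 60 young people living with HIV (YPLH) and "potentially 30 treatment monitors, will be recruited for the pilot". Everyone comes from one clinic, and "All eligible YPLH will be recruited consecutively until our desired sample size is obtained". In the Randomized Controlled Pilot Phase section, "Participants not randomized to the Text-Based Adherence Game will receive the SOC condition as described above".

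The only step described for enrolling a monitor is consent by study staff. It appears in the open-trial procedures, which carry over to the pilot subject to open-trial feedback. No check of a proposed monitor against the list of pilot participants is described.

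**The concern.** The control arm is defined by not receiving the game, yet the monitor role is a second way into the game and no rule keeps controls out of it. A game-arm patient may name a friend, partner or sibling who attends the same clinic and has been randomised to standard of care. That person would then take part in the intervention during the comparison year. The reverse order is also open: a YPLH already acting as a monitor can be recruited later and randomised to standard of care.

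Either route would pull the arms together on adherence, attendance and viral load. The direction is towards no difference, in a pilot whose Power paragraph already concedes that power may be inadequate and looks only for a signal. The Data Analytic Plan has no step that would detect or describe such exposure.

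**Working it through.** **1. Test a standard-of-care participant against the rules.**

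| Rule | Result for a control |
|---|---|
| Reads English, speaks English or a clinic language | Met through the control's own entry criterion (1) |
| Patient agrees to this person | Depends on the game-arm patient |
| Knows the patient's HIV status | Met if the two have disclosed to each other |
| Has a cellphone | Met through entry criterion (5) |
| Able to consent | Met through entry criterion (6) |
| Exclusion (a) | Does not apply: it concerns another study, and being a monitor is part of this one |
| Exclusion (b) | Does not apply: the control has already consented |

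The criteria as written admit this person.

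**2. Reproduce the plan's figures.** Retention of 86% gives 60 × 0.86 = 51.6, which rounds to the stated 52. The allocation ratio is not stated. Sixty patients and up to 30 monitors suggest 1:1, so 30 per arm enrolled and 26 per arm analysed are assumed.

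The plan claims 80% power at alpha 0.05 for small to medium effects with three assessments. For the group-by-time interaction, with noncentrality f² × 52 × 3 / (1 − ρ) and sphericity assumed, the detectable f is 0.21, 0.18 and 0.14 at ρ = 0.3, 0.5 and 0.7. This agrees with the plan's description; ρ itself is not given.

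**3. Dilution.** If c controls act as monitors and each gains a share s of the game's effect, the arm difference shrinks by (c/30) × s. Power is recomputed with f = 0.18 (ρ = 0.5) multiplied by 1 − (c/30) × s.

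| c | Loss, s = 1 | Power, s = 1 | Loss, s = 0.5 | Power, s = 0.5 |
|---|---|---|---|---|
| 0 | 0% | 0.80 | 0% | 0.80 |
| 1 | 1/30 = 3.3% | 0.77 | 1.7% | 0.79 |
| 3 | 3/30 = 10% | 0.71 | 5% | 0.76 |
| 6 | 6/30 = 20% | 0.60 | 10% | 0.71 |

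If the exposed control is among 26 analysed, one person is 1/26 = 3.8% at full effect.

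**4. How many controls might this be?** The documents give no frequency, so these are illustrations only.

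- If all 30 monitors were random patients from the clinic's estimated 4,000, the expected number of controls is 30 × 30/4000 = 0.2.
- If one third of monitors (10) came from a pool of 200 to 800 patients of eligible age (both assumed), the expected number is 10 × 30/200 = 1.5 down to 10 × 30/800 = 0.4. The loss at full effect is then 1.5/30 = 5% down to about 1%.
- If each of 30 monitors had a 1%, 2% or 5% chance of being a control (assumed), the chance of at least one is 1 − 0.99³⁰ = 26%, 1 − 0.98³⁰ = 45% or 1 − 0.95³⁰ = 79%.

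At least one such case is therefore quite possible, while many are unlikely.

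**The case against.** A reader might infer that the control arm will be contaminated, and that the pilot could therefore miss a game that works. The documents do not support that.

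- **Frequency.** Nothing shows a control being named as monitor. The Modified Social Provisions Scale in Appendix 3 does list "2- Same-age or younger friend" as a main source of help, but treatment buddy is a separate option on the same list, as are parents and other family. The item does not show that monitors are peers, still less fellow patients. The adolescent focus group guide suggests that having a treatment monitor is already part of routine care, so many monitors may predate the game.
- **Incentive.** The game reward is for recruiting any monitor. It does not favour fellow patients.
- **Exposure.** What a monitor receives is not described. The reminders and the tracking of adherence, visits and viral load are aimed at the patient, and no section says a monitor gets them for their own care.
- **Size.** Losses of 10% to 20% need 3 to 6 of about 30 monitors to be controls who each gain the full effect.
- **Chance of notice.** Staff consent every monitor at one site with 60 participants, so an overlap might well be seen.

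All of this stands, and it limits the size of the problem. It does not close the gap, because no rule tells staff to refuse a control they recognise. The monitor list skips from (3) to (5), but other lists in that section also skip numbers, so this is not evidence either way.

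An objection to the remedy also stands. If a nominee is visibly refused after a check of the participant list, the nominating patient could infer that the nominee is enrolled and so has HIV. That would work against the confidentiality commitments under Data Storage and Protection and Protection Against Risk.

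**Conclusion.** The gap is real: as written, the criteria allow a standard-of-care participant into the game as a monitor, and allow a monitor to be randomised to standard of care later. The consequence is conditional and probably small. Each exposed control costs about 3% of the arm difference at full effect and about 2% at half effect, always towards no effect. With the one or two exposed controls that the illustrations make plausible, the total loss is a few percent.

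This rests on 1:1 allocation with 30 per arm, an assumed share of the effect passing to a monitor, and assumed frequencies that the documents neither confirm nor rule out. The conclusion that a working game would be read as giving no signal does not follow at these values. The point merits a change because the bias is avoidable and the rule is cheap, not because it threatens the pilot. It is based on the available text, which lacks the body of the Data and Safety Monitoring Plan.

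**What to change.** - Add to the treatment monitor criteria: *not enrolled in the randomized pilot* (either arm).
- Add to the pilot exclusions: *has served as a treatment monitor in this study*. This covers the reverse order.
- Have staff who already hold the master list make the check privately, at the nominee's own consent visit. The Project Coordinator both holds the list and conducts consent, so access need not be widened.
- If the nominee is not eligible, tell the nominating patient only that this person will not be taking part. Use the same wording for every nominee who does not proceed, whatever the reason. The patient may name someone else or have the assigned peer educator already provided under Inclusion criteria.
- Record any monitor later found to be a pilot participant, so that the number can be reported.

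The cost is two sentences in the criteria and one check per monitor. A few patients lose their first choice of monitor, and a few YPLH who have served as monitors cannot enter the pilot. Staff must handle refusals so that they disclose neither enrolment nor HIV status. The rule does not stop friends in opposite arms from sharing game content informally; it closes only the formal route.

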on Centers for Disease Control and Prevention guidelines (44) led by a bachelors-level clinic counselor, as needed contact with counselors, and access to a clinic social event held once per year. They will then be shown the game by a trained RA. The basic elements of the game will be demonstrated and YPLH will have an opportunity to interact with the system, with study staff, to build interest and understanding. Participants will be asked permission to enroll a treatment buddy to participate in the game as well. This person will be consented by study staff. The game also pairs participants with a peer educator who has shown good medical adherence by clinic report and is trained to provide phone peer support. Three iterations of increasing game length (two, four, and eight weeks) and number of participants ($n = 6, 8$, and 10) will test game prototypes. After each iteration participants will be assessed with a semi-structured cognitive interview (45) to gauge participants' opinions of the game, and its clinical utility, relevance, strengths and weaknesses, ease of use, and ability to capture their experiences (See Appendix 1 for interview guide). Audio from cognitive interviews will be digitally recorded and transcribed. They will also complete quantitative measures for similar feedback. In addition, participants will be assessed before and after the third iteration on main study variables to explore shifts in our primary and secondary outcomes. Information gained after each iteration will be used by research staff to alter the game. Study staff will also contact participants after they enroll via a phone call to trouble shoot problems playing the game. YPLH will be remunerated with an allowance of 40 Cedis for each assessment. They will also be given 40 Cedis worth of prepaid phone credits to send text messages. Treatment monitors will be compensated 40 Cedis.

[figure not shown]

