Hypothesis One (Aim 1). The Text-Based Adherence Game will be feasible, appealing, and useful. YPLH in the third open trial iteration of the Text-Based Adherence Game will show shifts in primary and secondary outcomes in the expected directions from pre-post assessments.

Hypothesis Two (Aim 2). Compared to participants in the control group, participants in the Text-Based Adherence Game will show at 6 and 12 months post-intervention: improved ART adherence, clinic attendance, biologic functioning (lower

Figure 5. Assessment Schedule

HIV viral load, higher CD4 count), and shifts in secondary outcomes (social support, self-efficacy, etc.) consistent with adherence promotion. Repeated measures ANCOVAs will be used to test differences over time between study conditions on each outcome variable. Missing data will be handled using multiple imputation. Potential imbalance between treatment conditions on baseline characteristics will be addressed using inverse probability of treatment weights (51). Power: As this is a pilot study and the impact of the intervention is not known, there may not be adequate power to determine its efficacy; also, pilot studies are not designed to provide accurate estimates of effect sizes upon which to base large trials(52). However, the small pilot may provide a “signal” of impact on its primary outcomes and we will examine the effects of the intervention on secondary outcomes based on Social Action Theory. We assume that retention over one year is at least 86% based on past studies conducted in Ghana (31, 53) thus 52 cases of the 60 enrolled in the pilot are available for analysis. Power analyses were run with G*Power 3(54). The model assumed 3 assessments with 52 individuals. The analyses with alpha of 0.05 and power 0.80 will be able to detect small to medium effects.

DISSEMINATION OF RESULTS

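### Game monitoring is listed as a retention technique but exists only in the game arm, so effort to obtain the 6- and 12-month assessments can differ by arm

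*Combined protocol and SAP*

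**What the plan says.** The paragraph headed Sample, site/recruitment, and retention covers both phases of the project and ends with one list: "Retention techniques: routinely updating contact information, reminder phone calls, online monitoring of game interactions, maintaining records of friend/family contacts", and an emergency contact. It does not separate the open trial, where everyone plays, from the pilot, where only one arm does.

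Under Training of Research Assistants, Fidelity Monitoring, and Supervision, which describes the open trial, a team member is to follow participants' "game activity daily via the system" (that is, through the system's website). The open-trial procedures add: "Study staff will also contact participants after they enroll via a phone call to trouble shoot problems playing the game". The Randomized Controlled Pilot Phase section carries these over with a qualifier: "The same procedures will also be used pending open trial feedback". On the comparator it says: "Participants not randomized to the Text-Based Adherence Game will receive the SOC condition as described above". Both arms are assessed at baseline, 6 months and 12 months.

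The Data Analytic Plan gives one retention figure for the whole pilot: "We assume that retention over one year is at least 86% based on past studies conducted in Ghana". It handles missing data by multiple imputation, with no imputation model, missingness assumption or sensitivity analysis stated. Its inverse probability weights are for baseline imbalance, not for attrition.

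**The concern.** A retention technique is a means of getting outcome data. If one such technique can operate only in the game arm, the chance of obtaining a follow-up assessment may depend on assignment for a reason unrelated to the game's effect on adherence.

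Two things are at stake. First, if the people found in one arm but lost in the other differ in outcome, the comparison at 6 and 12 months is distorted. The pilot requires a recent detectable viral load, and the Background describes this age group as having the highest risk of leaving care, so a link between loss and outcome is plausible. Second, retention is itself something a pilot should learn about. A difference between arms could reflect the game, the extra tracing, or both, and the plan gives no way to separate them.

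**Working it through.** **1. The plan's own figure.** 60 × 0.86 = 51.6, rounded to 52, which agrees with the plan (52/60 = 86.7%). The figure is pooled, so it is compatible with equal or unequal losses by arm.

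**2. Which techniques can work in which arm.**

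| Technique | Game arm | Control arm |
|---|---|---|
| Contact updates | possible | possible |
| Reminder calls | possible | possible |
| Watching game play online | possible | not possible |
| Friend and family records | possible | possible |
| Emergency contact | possible | possible |

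Four of the five can be applied to everyone; one cannot. For none of them does the text fix a schedule or a number of attempts, or require equality between arms.

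**3. Which outcomes depend on attending** (Assessments and Measures, under Design Considerations).
- The 30-day and four-day self-reports of adherence are completed on the computer in the clinic, so they need the visit.
- Viral load is taken from the chart. It needs the visit only when there is no result from the preceding 3 months.
- CD4 count and visits kept or missed come from the chart, and abstraction does not in itself need the participant present.

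**4. Illustration of size.** The documents give no retention by arm and no outcome rates for those lost. Assumptions: 1:1 allocation with 30 per arm (the ratio is not stated), about 86% retained overall, no true effect, completers only.

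*Viral suppression.* Let p = 0.50 be the true proportion in both arms, q the proportion suppressed among those lost (0.20 or 0.30), and r the retention. The observed proportion is (p − (1 − r) × q) / r. Example with r = 0.93 in the game arm, r = 0.79 in controls and q = 0.20:
- game: (0.50 − 0.07 × 0.20) / 0.93 = 0.523
- control: (0.50 − 0.21 × 0.20) / 0.79 = 0.580
- difference: −5.7 points

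*Continuous outcome.* Suppose half of each arm is hard to retain, that half has a mean g SD worse, and all losses come from it. The false difference is 0.5 × g × (1/r_game − 1/r_control). For 0.90 and 0.82 with g = 1.0: 0.5 × (1.111 − 1.220) = −0.054 SD.

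| Retention, game / control | Suppression, q = 0.20 | Suppression, q = 0.30 | Continuous, g = 0.5 | Continuous, g = 1.0 |
|---|---|---|---|---|
| 86% / 86% | 0 | 0 | 0 | 0 |
| 90% / 82% | −3.3 points | −2.2 points | −0.027 SD | −0.054 SD |
| 93% / 79% | −5.7 points | −3.8 points | −0.048 SD | −0.095 SD |
| 97% / 75% | −9.1 points | −6.0 points | −0.076 SD | −0.151 SD |

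Negative values run against the game.

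**5. Direction.** The sign depends on the assumptions. Swapping the third row (79% game, 93% control) gives +5.7 points at q = 0.20. The sign also flips if those lost do better than those retained.

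**The case against.** A reader might infer that a game participant who goes quiet is noticed within a day and then called by staff, while a control is not. The documents do not support that. Daily monitoring appears under fidelity and supervision of the open trial, and no text says that inactivity triggers anything. The telephone call follows enrolment and concerns problems with play. The peer educator and treatment monitor belong to the intervention, not to tracing. The carry-over to the pilot is also conditional on open-trial feedback.

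Other points in the plan's favour stand. Four of the five techniques can serve both arms. The locator form asks for three friends or relatives and is not tied to an arm. Visit times and assessment payments are the same. Detailed call schedules may sit in the operating procedures that the protocol says will be written. Several outcomes come from the chart. Multiple imputation would remove the bias if the observed data explained the missingness.

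The illustrated distortion is also small beside sampling error. With 28 and 24 analysed and proportions 0.523 and 0.580, the 95% half-width is 1.96 × √(0.523 × 0.477/28 + 0.580 × 0.420/24) = 0.27, or 27 points. The plan itself disclaims adequate power.

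These points limit the size and certainty of the problem but do not remove it. The protocol itself classes an arm-specific tool as a retention technique for a paragraph that includes the pilot, and no text found offsets it. Sampling error also does not make a systematic difference in follow-up harmless, and it does nothing for the interpretation of retention.

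**Conclusion.** The point holds in a limited form: as written, retention effort can differ by arm, which can bias visit-dependent outcomes and blurs any retention difference. Neither size nor direction can be taken from the documents. If controls with poor outcomes were lost more often, the bias would run against the game. The 2 to 9 points and 0.03 to 0.15 SD above rest wholly on the stated assumptions and ignore the planned imputation.

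A reader might infer a firmer and larger bias hiding a benefit. Take 12 of 30 suppressed in each arm and everyone lost unsuppressed: 28 and 24 retained gives 12/28 = 42.9% against 12/24 = 50.0% (−7.1 points), and 29 and 23 gives 12/29 = 41.4% against 12/23 = 52.2% (−10.8 points). That is a worst case among completers. Nothing in the documents supports those splits, that suppression rate or that dropout pattern, and viral load will often be available from the chart.

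The text under the Data and Safety Monitoring Plan heading was not available to check for an offsetting rule.

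**What to change.** For the pilot, state that monitoring of game play is part of intervention delivery and fidelity only, and is not used to trace participants for assessments. Apply the same contact updates, reminder calls and missed-assessment tracing steps to both arms, with the same number of attempts, timed to the 6- and 12-month assessments. Report retention and contact attempts by arm.

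Calls between assessments need not be added; they would put extra contact into the standard-of-care comparator. The game's own messages and supporters would still differ by arm, as they should. Their effect on retention is then part of the intervention rather than of study follow-up.

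The cost is protocol and procedure wording and a simple log of contact attempts. Sample size and visits do not change. The downside is the loss of one retention cue in the game arm, so overall retention could be slightly lower.
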